Data will be generated as the difference in response between the control, non-treated site and the active treatment site within in each subject.

ANOVA and pairwise t-tests will be used to compare CTY-5339-A treatment groups to the CTY-5339-CB treatment group.

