8.4 Hypothesis

The following hypotheses will be tested to analyze the primary outcomes of the study:

- The null hypothesis that the duration of anesthesia (PPT and QST Heat) for the one spray CTY-5339-A group is the same as the corresponding duration for the CTY-5339-CB one spray group will be tested against the alternative hypothesis that the means are not equal.

The following hypotheses will be tested to analyze the secondary outcomes of the study:

- The null hypothesis that the duration of anesthesia (PPT and QST Heat) for the two spray CTY-5339-A group is the same as the corresponding duration for the CTY-5339-CB one spray plus CTY-5339-P one spray group will be tested against the alternative hypothesis that the means are not equal.
- The null hypothesis that the onset of anesthesia (PPT and QST Heat) for the CTY-5339-A groups is equal to the corresponding onset for CTY-5339-CB group will be tested against the alternative hypothesis that the means are not equal.
- The null hypothesis that the onset time until the first responder event (PPT and QST Heat) for the CTY-5339-A groups is equal to the corresponding onset time until a first responder event for CTY-5339-CB group will be tested against the alternative hypothesis that the event times are not equal.
- The null hypothesis that the duration time until the first non-responder event (QST and PPT) for the CTY-5339-A groups is equal to the corresponding duration time until the first non-responder event for CTY-5339-CB group will be tested against the alternative hypothesis that the event times are not equal.

The predicted outcome is that CTY-5339-A when locally applied to cheek mucosal tissue in the mouth will have an onset comparable to the fastest constituent, benzocaine, and a prolonged effect comparable to the longest acting constituent, tetracaine, of the combination product. The study also is designed to demonstrate that both the CTY-5339-A one and two-spray dosages are safe. (The assumption is made that benzocaine has a faster onset of action than tetracaine HCl.)

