9. SUMMARY OF STUDY DESIGN

This is a single-dose, double-blind and single-center study with an active control treatment. All subjects will remain at the study center for each of the two 60 minute test sessions. The volunteer subjects will be tested at two different test sessions separated by 4-14 days and serve as their own control.

The study will include 76 subjects with 60-minute evaluations at each test session.

At each session, a circular area of approximately 1 inch in diameter will be isolated on one side of the cheek. Each session will use a different side of the cheek. The possible sequences of treatments at the two sessions are:

Session 1		Session 2	
Formulation	Sprays	Formulations	Sprays
CTY-5339-A	1	CTY-5339-CB	1
CTY-5339-A	2	CTY-5339-CB	1
CTY-5339-CB	1	CTY-5339-A	1
CTY-5339-CB	1	CTY-5339-A	2

(To maintain double-blind conditions, the CTY-5339-CB subjects in two spray sequences will also receive one spray with the vehicle control (CTY-5339-P) just outside the circumscribed area. A third party not involved with evaluating subjects will administer the drug.)

For PPT, evaluations will be done at 1-minute intervals following drug administration for the first 5 minutes to capture onset of anesthesia. Starting at 5 minutes after drug administration, both PPT and QST will be done at 5-minute intervals up to the one hour time point. Once onset has occurred, if there is no analgesia at two consecutive evaluation time points (from 10 minutes onward), the session will be discontinued. In addition, if onset of analgesia has not occurred by 10 minutes post dose, the subject will be considered a treatment failure and no further assessments will be made.

PPT: The PPT will be assessed, using a 90-mm, 26-gauge pencil-point spinal needle (Polymedic or equivalent; Temena S.A., Bondy, France or its equivalent). At each post dosing time point, PPT will be assessed in 3 repetitions on the non-treated site using a 0-10 Numerical Rating Scale (NRS) with "0" as no pain and "10" as severe pain. PPT will then be assessed in 3 repetitions on the treated site. These assessments will be compared to the contra-lateral, non-treated site as "No pain", "Less Pain" or "Similar/More Pain". "No Pain" or "Less Pain" at an application site will be recorded as presence of analgesia/anesthesia ("Responder").

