13.5 Statistical Methods for Efficacy Evaluations

The primary efficacy analyses will be based on Modified Intent-to-Treat Population. The key comparisons will include:

1. CTY-5339-A, one spray versus CTY-5339-CB, one spray

The co-primary efficacy variables are duration of effect as measured by PPT and QST Heat. Duration of effect is defined as the time (in minutes) from onset to treatment failure (*i.e.*, for PPT, an assessment of “Same/More” pain, and for QST, the average heat temperature is greater than the average heat temperature at Baseline (non-treated cheek), up to the 60-minute time point (at two consecutive time points). For those discontinuing from the study for any other reason, the time to treatment failure will be censored at the last assessment time.

The secondary efficacy variables include:

- Duration of effect (PPT and QST) for CTY-5339A two sprays versus CTY-5339-CB, one spray plus CTY-5339-P one spray

- Duration of effect (PPT and QST) for CTY-5339A two sprays versus CTY-5339-A one spray
- Onset of anesthesia in minutes for PPT and QST Heat
- Percentage of responders at each time point for PPT and QST Heat for both onset and duration

Continuous variables will be analyzed via an ANOVA model with treatment effects at each of assessed time points. Pairwise comparisons for variables related to percentages will be analyzed via chi square tests. The 95% confidence intervals of the treatment differences will be presented using normal approximation with continuity correction, if appropriate. Pairwise comparisons for time-to-event related variables will be analyzed via a log rank model with treatment effects. Median time to event will be estimated and the 95% confidence intervals for the median will be presented, if appropriate.

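### The primary analysis of duration is stated inconsistently (means and t-tests, or log-rank), and no rule covers a subject who is still numb at 60 minutes

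*Combined protocol and SAP*

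**What the plan says.** **Endpoint.** Section 13.5: "Duration of effect is defined as the time (in minutes) from onset to treatment failure", "up to the 60-minute time point (at two consecutive time points"). Section 9 sets the schedule: from 5 minutes, "both PPT and QST will be done at 5-minute intervals up to the one hour time point", with pin prick also each minute before that. It limits onset as well: "if onset of analgesia has not occurred by 10 minutes post dose, the subject will be considered a treatment failure".

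**Censoring.** The one rule, in 13.5, is "For those discontinuing from the study for any other reason, the time to treatment failure will be censored at the last assessment time".

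**Hypothesis and test.** Four statements bear on duration:

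- Section 8.4, primary: equality of duration "will be tested against the alternative hypothesis that the means are not equal". No test is named.
- Section 8.4, secondary: time to the first non-responder event "will be tested against the alternative hypothesis that the event times are not equal".
- Synopsis, statistical analysis: "ANOVA and pairwise t-tests will be used to compare CTY-5339-A treatment groups to the CTY-5339-CB treatment group". The sentence names no endpoint.
- Section 13.5: ANOVA for continuous variables; log-rank with median times and confidence intervals for time-to-event variables. Duration is not assigned to either class.

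**Population.** The primary analysis uses the mITT population (13.2), which keeps eligible subjects who completed both 60-minute sessions. Subjects still numb at 60 are therefore in it.

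**The concern.** The trial asks whether CTY-5339-A numbs for longer than benzocaine alone. A session in which the cheek is still numb at 60 minutes shows only that the duration is at least 60 minus onset. A comparison of plain means has no place for such a value except as an exact duration. The product that lasts longer would reach this ceiling more often, so it would lose more of its true duration. Both co-primary endpoints are affected.

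A log-rank analysis does not settle the matter by itself, because the plan never says that these subjects are censored. An analyst could code 60 minutes as an event or as censored and cite the plan for either. A first failing reading at 60 has the same problem: failure needs two consecutive time points, and none follows.

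**Working it through.** **What can be reproduced.** The per-endpoint alpha is 0.10/2 = 0.05, as in 13.6. Exposures are 76 × 2 = 152 = 38 + 38 + 76, as in the synopsis. The one-spray comparison therefore rests on 38 subjects, each tested on both products. Section 13.1 gives no effect size, SD or power, so the sample size of 76 cannot be checked, and the share still numb at 60 cannot be derived.

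**The ceiling.** Recordable duration is at most C = 60 − onset.

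- Pin prick: onset from 1 to 10 minutes, so C runs from 59 to 50.
- Heat: first reading at 5 minutes, so C runs from 55 to 50.
- Confirmed failure needs two readings, so the last pair that can confirm it is 55 and 60 minutes.

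**Effect on a difference in means.** Let T be the true duration. If ceiling values are taken as exact, the analysis compares E[min(T, C)] instead of E[T]. For exponential T with mean m,

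E[min(T, C)] = m(1 − e^(−C/m)), and the share still numb is e^(−C/m).

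Example with assumed means of 20 (CTY-5339-CB) and 30 (CTY-5339-A), C = 55:

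- CB: 20 × (1 − e^(−2.75)) = 18.72
- A: 30 × (1 − e^(−1.833)) = 25.20
- Recorded difference 6.5, true difference 10, ratio 0.65

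The table repeats this at C = 55 and adds a Weibull distribution with shape 2, which has less spread. All means are assumptions.

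| Means CB v A | True difference | Exponential: recorded (ratio); numb at ceiling CB v A | Weibull: recorded (ratio); numb at ceiling CB v A |
|---|---|---|---|
| 15 v 20 | 5 | 4.1 (0.82); 3% v 6% | 5.0 (1.00); under 1% in both |
| 20 v 30 | 10 | 6.5 (0.65); 6% v 16% | 9.4 (0.94); under 1% v 7% |
| 30 v 45 | 15 | 6.5 (0.44); 16% v 29% | 10.0 (0.67); 7% v 31% |
| 40 v 60 | 20 | 6.1 (0.31); 25% v 40% | 8.4 (0.42); 23% v 52% |
| 60 v 90 | 30 | 5.1 (0.17); 40% v 54% | 5.1 (0.17); 52% v 75% |

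Lognormal durations (log-SD 0.4 to 0.6, C = 58) show the same pattern. The shortfall is 0–3% for medians 10 v 15, 0–5% for 10 v 20, 12–31% for 20 v 40, 26–44% for 25 v 50, and 40–56% for 30 v 60.

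**Dependence on onset.** Take one exponential duration with mean 60. With onset at 1 minute the recorded mean is 60(1 − e^(−59/60)) = 37.6. With onset at 10 minutes it is 60(1 − e^(−50/60)) = 33.9. The gap of 3.6 minutes comes from onset alone.

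**Power.** Simulation of 38 pairs, 5-minute grid, C = 55, no within-subject correlation, two-sided 0.05, 1,500 runs:

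| Scenario | Paired t-test, ceiling taken as exact | Log-rank, censored at ceiling |
|---|---|---|
| Exponential 20 v 30 | 0.35 | 0.39 |
| Exponential 40 v 60 | 0.25 | 0.29 |
| Weibull 20 v 30 | 0.87 | 0.92 |
| Weibull 40 v 60 | 0.66 | 0.81 |

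**No true difference.** If the arms share the same duration and onset distributions, min(T, C) has the same distribution in both, and the expected difference is zero.

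**The case against.** The strongest reply is that 13.5 already plans the right analysis. It defines duration as a time to failure, speaks of censoring, and supplies a log-rank test with medians. A censoring rule is of no use to a t-test, so duration is most naturally a time-to-event variable. This stands as a plausible reading. It does not settle the plan, because 8.4 gives means to the primary duration hypothesis and reserves event times for a separate secondary one. Nor does it supply the missing rule for completers.

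A reader might infer more: that 8.4 prescribes a t-test, that the plan does treat the 60-minute ceiling as a true duration, and that the co-primary difference will be understated. The documents do not support this. Section 8.4 names no test, and the t-tests appear only in the synopsis. Treating the ceiling as exact is one of two readings. Understatement needs a true advantage and enough subjects numb at 60, and the documents give neither.

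Two further replies hold in part. Duration is defined within the 60-minute window, so a window-limited mean is a legitimate target; but the plan does not declare one, and a limit that moves with onset is not a clean one. And the error is conservative, in a proof-of-concept study that would accept a clear trend (13.1). That limits the harm to the estimate and to power, which in most of the simulated cases falls only modestly.

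**Conclusion.** The concern holds as an unresolved conflict plus a missing rule. Section 8.4 and the synopsis point to means, 13.5 points towards log-rank, and no text gives the status of a completer without confirmed failure or of a first failure at 60.

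The harm is conditional on the means reading, on CTY-5339-A truly lasting longer, and on a material share of sessions reaching the ceiling. The mean difference then shrinks, power falls somewhat, and recordable duration depends on onset. Across the assumed exponential and Weibull cases the recorded difference is 100% down to 17% of the true one. These are illustrations and do not forecast this trial. The false-positive rate is not raised when the arms differ in neither duration nor onset.

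This should be settled before unblinding, because both co-primary endpoints are affected and the choice could otherwise be made with results in view.

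**What to change.** 1. In 8.4, the synopsis and 13.5, name one primary analysis of duration: a time-to-event comparison that respects the within-subject pairing, with Kaplan-Meier medians. A plain log-rank test ignores the pairing.
2. In 13.5, state that a subject without confirmed failure by 60 minutes is censored at the last assessment.
3. Define the status of a first failing reading at 60 minutes.
4. Report by treatment the number still numb at 60.
5. If a mean is kept, declare it a restricted mean with a stated limit and the reason for it. A limit of 50 minutes after onset can be reached by every subject with onset by 10 minutes, but it narrows the contrast: for lognormal medians 25 v 50 the gap to the unrestricted difference is 37–53%, against 26–44% at 58. That is acceptable only if the restricted mean is the declared target.

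The cost is wording in the three sections; no visit or measurement changes. The headline estimate becomes a median or a restricted mean instead of a plain mean.

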ESTIMATED DURATION OF SUBJECT PARTICIPATION IN THE STUDY:

The subjects will be tested on two separate occasions. Each session will take approximately two hours total time; however, the actual efficacy testing will take 60 minutes. There will be 4-14 days spacing between visits. A phone follow-up will occur 3 days (\pm 1 day) and 15 days (\pm 2 days) after the subject completes Sessions 1 and 2, respectively. If there are any adverse side effects, at the discretion of the PI, the subject may be asked to return to the study site for evaluation.

DURATION OF STUDY:

The study will be completed when the last subject completes the last follow up phone call. The expectation is that the study will be completed within 4-6 months of the first subject entry.

NUMBER OF SUBJECTS:

Up to 150 male and female subjects will be screened in order to enroll up to 76 ASA Category I or II subjects. The total number of exposures to study medication will be 152 (76 subjects x 2 exposures). Each of the CTY-5339-A treatment regimens will have 38 exposures and the CTY-5339-CB will have 76 exposures.

SAMPLE SIZE DETERMINATION:

The sample size was selected based on evaluating a reasonable number of subjects to determine whether CTY-5339-A has a longer duration of action than CTY-5339-CB, which contains 14.0% benzocaine only.

DOSAGE:

(specific gravity is slightly less than 1; therefore 200 μ L is an approximate volume.)

CTY-5339-A 1-metered spay = 200 mg total (\approx 200 μ L)
Benzocaine 28 mg + Tetracaine HCl 4 mg

CTY-5339-A 2-metered spays = 400 mg total (\approx 400 μ L)
Benzocaine 56 mg + Tetracaine HCl 8 mg

CTY-5339-CB = 200 mg (\approx 200 μ L)
Benzocaine 28 mg

INCLUSION CRITERIA:

- a. Male and female subjects between 18-75 years of age with a Body Mass Index (BMI) \leq 32;
- b. Subjects are ASA Category I or II and are in good physical health as judged by physical and laboratory examinations;
- c. Subjects with normal appearance of the oral mucosal tissues;
- d. At screening and at Baseline during Session 1, subjects with PPT scores on both cheeks of at least "3" (on a 10 point NRS) on the last 2 of 3 readings, 1 of which must be a score of at least "4";
- e. Subjects with mean QST Heat sensation temperature assessments

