APPENDIX 2: CRITERIA FOR A “RESPONDER”

PPT:

Based on “No Pain” or “Less Pain” response to the pain stimulus at each observation time when compared to the non-treated site, subjects will be classified as “Responders” or “Non Responders”. At each observation, 3 pin pricks will be performed at each site (first on the non-treated cheek and then on the treated cheek). The first pin prick will not be used for analysis. Of the remaining two pin pricks, the one with the most severe pain rating will be used for the data analysis. If the most severe pain rating at that time point is “No Pain” or “Less Pain”, then the subject at that time point is a “Responder”.

QST:

The actual temperature data will be recorded at each time point. Temperatures will be recorded for "first sensation of tingling, warmth, heat, or pain". Scores will be censored at 51°C, if no response is obtained. If the average heat sensation temperature at each time point is greater than the average heat sensation temperature at Baseline, then the subject at that time period will be considered a “Responder”.

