13.1 Sample Size Determination

This study is a proof-of-concept study to determine if CTY-5339-A one or two sprays have a relevant efficacy advantage over CTY-5339-CB. Although a statistically significant difference is desirable, a clear-cut trend for increased duration of analgesia would be acceptable. A sample of 76 subjects in the efficacy evaluation part was felt to be adequate for the purposes of this proof-of-concept study.

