13.3 Demographic Data and Baseline Comparability

Quantitative demographic data will be described by summary statistics (number of subjects, mean, standard deviation, median and range). The number and percentage of subjects will be presented for categorical variables. No formal statistical comparison

between the treatment groups will be performed. Demographic data summary will include age, gender and race. These data will be presented for the overall safety population only, unless the sample sizes for ITT and MITT subject populations are very different from that of safety population (differ by more than 3 subjects). In this case, demographic data will be presented for that population. Baseline efficacy assessments will also be presented by treatment group.

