13.6 Multiple End Points and Multiple Comparisons

Duration of Effect, as assessed by PPT and QST Heat are co-primary efficacy parameters. In order to control the overall significance level for the two primary endpoints, the total alpha level of 0.1 is Bonferroni adjusted to $0.10/2 = 0.05$ (since this is a proof of concept study, the total alpha level of 0.1 instead of 0.05 has been selected). The study will be considered successful if either of the two primary endpoints is statistically significant.

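### The session's own QST Baseline sets the QST failure line but enters no efficacy model, so avoidable noise stays in the QST co-primary duration

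*Combined protocol and SAP*

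**What the plan says.** **Measurement.** The synopsis (QST-Heat) and section 11.2.2 require three heat readings on the cheek about to be treated, before dosing in each session. The last two are averaged, and that mean may not exceed 48.5°C.

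**Role in the endpoint.** Appendix 2 counts a subject as a QST responder on this condition: "If the average heat sensation temperature at each time point is greater than the average heat sensation temperature at Baseline". The synopsis (Efficacy Measurements) declares QST failure once the mean temperature has come back to Baseline or lower on two successive assessments.

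**Role in the analysis.** Section 13.5 states: "Continuous variables will be analyzed via an ANOVA model with treatment effects at each of assessed time points". Time-to-event variables get a log rank test on treatment, and percentages get chi-square tests. The synopsis names ANOVA and pairwise t-tests, with no covariate. The only use of Baseline efficacy data in the analysis section is descriptive (13.3): "Baseline efficacy assessments will also be presented by treatment group".

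**Size and success rule.** The synopsis gives the exposures: "Each of the CTY-5339-A treatment regimens will have 38 exposures and the CTY-5339-CB will have 76 exposures". Section 13.1 justifies the sample size by judgement: "A sample of 76 subjects in the efficacy evaluation part was felt to be adequate for the purposes of this proof-of-concept study". Under 13.6 each co-primary is tested at 0.05, and significance on either one makes the study a success.

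**The concern.** It is easy to assume that an endpoint defined relative to Baseline is already adjusted for Baseline. Here the reverse happens. The reference line is the mean of two readings, fixed for the session. If that mean reads high by chance, every later assessment is judged against too high a line and the QST duration comes out short. If it reads low, the duration comes out long. The definition thus carries Baseline reading error into a co-primary, and a treatment-only model leaves it in the residual even though its source has been recorded.

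The treated-minus-untreated difference mentioned in the synopsis does not help, because during sessions QST is done on the treated cheek only.

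At stake is precision in a comparison with 38 one-spray CTY-5339-A exposures. Since either co-primary can carry the study, noise in QST duration lowers the chance of success.

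**Working it through.** **1. The plan's own figures.** Alpha per endpoint is 0.10/2 = 0.05 (13.6), two-sided (8.4). Exposures are 76 × 2 = 152 = 38 + 38 + 76. Both agree with the text. The figure of 76 cannot be reproduced, because no effect size, SD or power is given. At 80% power, 38 subjects detect (1.960 + 0.842)/√38 = 0.45 SD of the within-subject difference, or 2.802 × √(2/38) = 0.64 SD if the sessions are treated as independent.

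**2. How Baseline error enters.** QST is assessed every 5 minutes to 60, so one Baseline error bears on 60/5 = 12 comparisons. Let s be the SD of a single reading (assumed 0.7, 1.0 or 1.5°C). The error variance of a two-reading mean is s²/2. Assume also a between-subject SD of 2°C and a session/cheek SD of 0.7°C. The share of Baseline variance that is reading error is then:
- across subjects, (s²/2)/(2² + 0.7² + s²/2): 0.245/4.735 = 5%, 0.5/4.99 = 10%, 1.125/5.615 = 20%;
- in the A minus CB difference, s²/(2 × 0.7² + s²): 0.49/1.47 = 33%, 1/1.98 = 51%, 2.25/3.23 = 70%.

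A person's stable threshold moves the response curve and the failure line together, so it says little about duration. Reading error moves the line alone. This is why a Baseline covariate does little in a between-groups ANOVA and more in a within-subject one.

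**3. Simulation.** Further assumptions: true Baseline mean 42°C, peak effect 6°C, decay constant 24 minutes for A and 16 for CB, readings capped at 51°C, and failure defined as in the synopsis. Share of QST-duration variance removed by Baseline:

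| Single-reading SD | Treatment-only ANOVA | A minus CB difference |
|---|---|---|
| 0.7°C | 2% | 11% |
| 1.0°C | 4% | 21% |
| 1.5°C | 10% | 35% |

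In the within-subject form, each 1°C of Baseline difference shifts duration by about 3 to 6 minutes. Null rejection rates were about 4 to 6%. About 50 to 86% of sessions had not failed by 60 minutes.

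**4. What that is worth.** The standard error is multiplied by √(1 − share removed), and the equivalent sample size is 38/(1 − share removed).
- Treatment-only ANOVA: √0.98 = 0.99 to √0.90 = 0.95; 38/0.98 = 38.8 to 38/0.90 = 42.2.
- Within-subject: √0.89 = 0.94 to √0.65 = 0.81; 38/0.89 = 42.7 to 38/0.65 = 58.5.

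The SD of the Baseline difference is √(2 × 0.7² + s²), which is 1.21°C at s = 0.7 and 1.80°C at s = 1.5. A one-SD chance imbalance in its mean over 38 pairs is therefore 1.21/√38 = 0.20°C to 1.80/√38 = 0.29°C. At 3 and 6 minutes per degree this moves the estimated difference in duration by 0.20 × 3 = 0.6 to 0.29 × 6 = 1.7 minutes.

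**5. Sensitivity to the assumptions.** A second set used between-subject SD 1 to 3°C, two-reading-mean SD 0.3 to 1.2°C, session shift SD 0 or 0.7°C and peak effect 4°C. Baseline removed 0 to 32% in the treatment-only ANOVA (12% or less once between-subject SD was 2°C or more) and 6 to 49% within subject. With 38 pairs, power in the within-subject form rose from 0.17–0.24 unadjusted to 0.24–0.39 adjusted, and null rejections stayed at 0.06 or below. Absolute power depends heavily on the assumed effect, so only the variance shares are carried forward.

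**The case against.** The strongest reply is that the plan as written loses little. Section 13.5 specifies treatment-only ANOVA and log rank, and nothing shows that the synopsis means paired tests by its pairwise t-tests. Against that analysis the covariate recovers 2 to 10%, worth 1 to 4 points of power in the simulations. The larger gain requires moving to a within-subject analysis, which is a separate gap. This stands. A reader might take 11 to 35% as the loss in the planned analysis; the documents do not support that.

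The model is a second difficulty. Duration is followed to 60 minutes with censoring, and a log rank test cannot carry a continuous covariate. Adjustment therefore means changing the model, not adding a term to it. This also stands.

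A reader might infer bias, since a chance Baseline imbalance feeds into the estimated difference. Sequence and cheek are randomised, so this is ordinary sampling variation already reflected in the standard error, and the null rejection rates agree.

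A reader might also point to QST temperature, where Baseline removed 11 to 86% of the variance at 30 minutes in a treatment-only ANOVA under the second set of assumptions. Temperature is not a listed endpoint; its analysis is only implied by the reference to each time point. In a within-subject comparison the figure was 0 to 31%.

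Finally, this is a proof-of-concept study for which 13.1 says: "Although a statistically significant difference is desirable, a clear-cut trend for increased duration of analgesia would be acceptable". That lowers the urgency, but it does not argue for discarding a measurement already in hand.

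**Conclusion.** The omission is real. A value collected before every dose, which defines a co-primary endpoint, is absent from every efficacy model. The consequence is lost precision in QST duration; neither bias nor an inflated type I error follows from it.

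The size cannot be fixed from the documents. Under the assumptions in step 3, Baseline removes about 2 to 10% of QST-duration variance in the treatment-only ANOVA and about 11 to 35% in a within-subject analysis. Other plausible assumptions widen these ranges to 0 to 32% and 6 to 49%.

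The argument rests on the failure rule in the synopsis and Appendix 2. Section 13.5 prints the inequality the other way round (failure when above Baseline) and ties it to the untreated cheek, which is not tested with QST in sessions. Until these passages agree, the covariate cannot be specified.

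**What to change.** 1. Reconcile the QST failure definition in 13.5 with the synopsis and Appendix 2, both in direction and in the cheek that supplies Baseline.
2. In 13.5, pre-specify the same-session treated-cheek Baseline QST (mean of the last two readings) as a covariate for QST duration, in a within-subject regression that handles censoring at 60 minutes. One option is a Cox model stratified by subject with Baseline as covariate. If duration is to be analysed as continuous, regress the A minus CB difference on the Baseline difference and test the intercept, accepting that durations cut off at 60 minutes are then treated as observed.
3. Keep the unadjusted analysis as a sensitivity analysis.
4. If QST temperatures are compared at each time point, include Baseline there too, as a secondary matter.

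Cost: no new data, one degree of freedom, and a regression model in place of the plain log rank test for this endpoint. In the stratified Cox model a subject with no observed failure in either session contributes nothing. With 50 to 86% of simulated sessions not failing, that should be weighed against a subject-frailty model before the choice is fixed.

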8.3.2 Secondary Outcome Measures

- Duration of anesthesia as measured by PPT and QST Heat for the two sprays of CTY-5339-A compared to the one spray of CTY-5339-CB plus one spray of CTY-5339-P

- Duration of anesthesia as measured by PPT and QST Heat for the two sprays of CTY-5339-A compared to the one spray of CTY-5339-A
- Onset of anesthesia for PPT and QST Heat
- Percentage of responders for PPT and QST Heat for both onset and duration
- Percentage of responders for PPT and QST Heat at each time point

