13.2 Analysis Populations

There will be three analysis populations:

Safety population: will include all randomized subjects who received the study medication. This population will be used for all safety summaries.

Intent-to-Treat (ITT) population: will include all randomized subjects who dosed with study medication and provided a Baseline assessment. All secondary efficacy analyses and summaries will be performed using this population.

Modified Intent-to-Treat (mITT) population: will include all randomized subjects who, as documented prior to the breaking of the study blind: (1) met all the inclusion and exclusion criteria and; (2) either completed the two 60 minute test sessions or returned to baseline values in all the evaluation tests. The primary efficacy analyses will be performed using this population.

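### Section 13.5 gives responder-percentage differences only a normal-approximation interval, which is erratic near 0% or 100% with 38 exposures per regimen, and names no paired interval for CTY-5339-A versus CTY-5339-CB

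*Combined protocol and SAP*

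**What the plan says.** Section 13.5 sets the test for responder outcomes: "Pairwise comparisons for variables related to percentages will be analyzed via chi square tests". The next sentence gives the interval: "The 95% confidence intervals of the treatment differences will be presented using normal approximation with continuity correction, if appropriate". Its position, and the continuity correction, show that it concerns percentages. The section does not say whether the final condition governs the correction or the presentation of the interval at all. It names no score, exact or paired alternative.

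The endpoint is secondary. Section 8.3.2 lists "Percentage of responders for PPT and QST Heat at each time point", and Section 13.5 words it as "Percentage of responders at each time point for PPT and QST Heat for both onset and duration". Section 13.2 assigns it to the ITT population: "All secondary efficacy analyses and summaries will be performed using this population".

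On numbers, the synopsis says: "Each of the CTY-5339-A treatment regimens will have 38 exposures and the CTY-5339-CB will have 76 exposures". On design, Section 9 says: "The volunteer subjects will be tested at two different test sessions separated by 4-14 days and serve as their own control". Each subject therefore receives one CTY-5339-A regimen and CTY-5339-CB. Only CTY-5339-A two sprays versus one spray compares different people.

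**The concern.** The standard error of a normal-approximation interval shrinks to zero as an observed percentage approaches 0% or 100%. Responder percentages are reported at every time point from 1 to 60 minutes for PPT and from 5 to 60 minutes for QST, so some may fall near an end. Both formulations contain 14.0% benzocaine, and Appendix 2 counts any reduction in pin-prick pain, or any rise above the Baseline temperature, as a response. Early rates could therefore be high in both arms. Late rates could be low for PPT as the effect wears off.

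The synopsis predicts an onset comparable to benzocaine. If every subject responded in both arms, an interval of a few points could be read as close agreement that 38 subjects cannot establish. In addition, an independent-groups formula applied to CTY-5339-A versus CTY-5339-CB would ignore the crossover.

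**Working it through.** **Inputs.** The method is from Section 13.5, with z = 1.960. The synopsis gives n = 38 per CTY-5339-A regimen and 76 for CTY-5339-CB, and the exposures add up: 76 × 2 = 152 = 38 + 38 + 76. CTY-5339-CB splits into 38 alone and 38 with vehicle if the sequences are balanced (an assumption). The plan states no responder rate, coverage or power, so there is no such figure to reproduce, and every true rate below is assumed.

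**Planned interval, independent groups.** d ± [z·√(p₁(1−p₁)/n₁ + p₂(1−p₂)/n₂) + ½(1/n₁ + 1/n₂)]. The correction is ½(1/38 + 1/38) = 1/38 = 2.63 points.

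**Everyone responds, 38/38 versus 38/38.** The standard error is 0, so the interval is 0 ± 2.6 points, or [0, 0] without the correction. For Newcombe, the Wilson lower limit for 38/38 is 38/(38 + 1.960²) = 90.8%, so the interval is ±(100 − 90.8) = ±9.2 points. The same holds for 0/38 in both arms.

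**Limits out of range, 38/38 versus 2/38.** d = 36/38 = 94.7 points. z·SE = 1.960 × √(0.0526 × 0.9474/38) = 7.1 points. The upper limit is 94.7 + 7.1 + 2.6 = 104.5% after rounding; Newcombe gives 98.5%.

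**Coverage.** Exact enumeration of two independent Binomial(38, p) samples:

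| True rates | With correction | Without |
|---|---|---|
| 100% vs 97% | 68.6% | 68.5% |
| 100% vs 95% | 85.7% | 85.5% |
| 99% vs 95% | 90.2% | 85.0% |
| 98% vs 95% | 93.2% | 85.2% |
| 100% vs 98% | over 99.9% | 53.5% |
| 99% vs 97% | over 99.9% | 76.4% |
| 98% vs 98% | over 99.9% | 99.4% |
| 95% vs 90% | 97.8% | 93.7% |
| 90% vs 80% | 97.5% | 94.3% |

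The low end mirrors these (3% vs 0% also gives 68.6%). The first row has a simple cause: the chance of 38/38 in the 97% arm is 0.97³⁸ = 31.4%. The ±2.63-point interval then misses the true 3 points, leaving 100 − 31.4 = 68.6%. At 100% versus 98% the true difference of 2 points lies inside ±2.63, so the same outcome counts as covered. That is why neighbouring rates differ so sharply.

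**Range.** Over a grid with both rates from 50% to 100% in steps of 0.25 point, minimum coverage with the correction is 84.0% if the higher rate is at most 99%, 94.7% if at most 97.5%, and 96.2% if at most 95%. About 0.5% of the grid falls below 93%. Without the correction the three minima are 57.6%, 85.3% and 92.4%. By symmetry the same holds with both rates below 50%. These minima do not extend to rates at opposite ends: 97.5% versus 2.5% gives 85.4% with the correction by the same enumeration.

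**Newcombe on the same grid.** Coverage is 99.9% at 100% versus 97%, 95.5% at 90% versus 80%, and at least 93.6% overall (minimum near 59% versus 50%).

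**Within-subject comparison.** With b and c discordant pairs out of 38, the paired normal-approximation interval has d = (b − c)/38 and SE = √{[(b + c)/38 − d²]/38}, plus 1/38 for the correction. Discordance of 3% and 0% gives 68.6% coverage, and 5% and 0% gives 85.7%. Pairing alone does not remove the boundary problem. If CTY-5339-CB were pooled (38 versus 76), coverage at 100% versus 97% is 90.1%.

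**The case against.** The strongest reply is that little depends on this interval. Responder percentages are secondary; Section 13.6 defines success by the two durations; Section 13.1 would accept a clear trend; and no equivalence margin for onset uses the interval. That stands, and it makes this an optional improvement.

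The premise can also be challenged. No expected rates are given. The protocol provides for subjects with no onset by 10 minutes, so early rates need not approach 100%. A QST responder is anyone above Baseline at all, so measurement variation could keep late rates off 0%. That stands too: rates near the ends are plausible but not established.

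The low coverage figures can reflect near misses. At 100% versus 97% the all-respond interval misses by 3.00 − 2.63 = 0.37 points; at 100% versus 95% the same outcome misses by 5.00 − 2.63 = 2.37 points. Where both true rates are 98%, the planned interval over-covers. This limits the practical harm. It does not justify ±2.6 points as a statement of uncertainty after 38/38 in both arms.

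A reader might infer that the planned interval generally collapses, or that its coverage is about 69%. The documents do not support either. The correction is part of the stated method, full collapse needs it to be withheld, and 69% belongs to one assumed corner with over-coverage close by.

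Finally, Newcombe is itself conservative near the ends, so choosing it is partly preference.

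**Conclusion.** The point holds as a minor one. With the correction and both rates on the same side of 50%, the planned interval is adequate unless a rate lies beyond about 97.5% or 2.5%. Past that its coverage jumps between about 69% and nearly 100% on small changes in the true rates, and it can return ±2.6 points where a score interval gives ±9.2. These coverage figures rest on assumed rates and on 38 evaluable subjects per regimen. The independent-groups calculation describes only CTY-5339-A two sprays versus one spray; for CTY-5339-A versus CTY-5339-CB the plan names no paired interval. It would be wrong to infer that the efficacy conclusion is at risk, because the co-primary durations and the success rule do not use this interval.

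**What to change.** Replace the interval sentence in Section 13.5 with:

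> Two-sided 95% intervals for differences in responder percentages will use a score-based method: the paired Newcombe interval for CTY-5339-A versus CTY-5339-CB within subject, and the independent-groups Newcombe interval for CTY-5339-A two sprays versus one spray.

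This removes the undefined condition on the present method and keeps limits within range. It costs one sentence and one option in the code. Intervals near 0% or 100% become wider and somewhat conservative. Since the chi-square sentence is left as it is, a paired interval for CTY-5339-A versus CTY-5339-CB may not always agree with that test, and the report should say so.
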